**Interleaving stimulation improving dyskinesia in Parkinson's
disease: randomized, double-blind, controlled trial**

2022.5.20

Version 1.5

Interleaving stimulation improving dyskinesia in Parkinson's disease: randomized, double-blind, controlled trial

Study protocol

1. Background

The clinical utility of deep brain stimulation (DBS) for the treatment of Parkinson's disease (PD) has been well established; however, there are a variety of adverse events, such as dyskinesia among subthalamic nucleus (STN) DBS recipients due to varied postoperative management. The artificial electrical signals of deep brain stimulation are delivered with four parameters; contact (0~3), frequency (Hertz - Hz), amplitude (voltage or current) and pulse width (microseconds, μ s). It has recently been reported that interleaving stimulation can be used effectively to treat motor symptoms while avoiding side effects.

Dyskinesia

Levodopa-induced dyskinesias (LIDs) are motor complications of Parkinson's disease. LID is characterized by progressive motor disability and may interfere with quality of life.

STN-DBS has also been demonstrated to provoke or exacerbate dyskinesia (stimulation-induced dyskinesia, SID). Previous studies have showed that the proportion of stimulation-induced dyskinesia is as high as 50% to 75%.

Both kinds of dyskinesias have variable phenotypes, including chorea, ballism, dystonia, myoclonus, or combination of any of these movements. SIDs are easily evoked in patients with severe preoperative LIDs.

In general, reducing the dosage of levodopa can improve LIDs post-operation. However, this approach will fail when dyskinesia is the result of stimulation. Available programming, such as interleaving stimulation could improve dyskinesias post-operation.

So, this study is designed as a prospective, **randomized, double-blind, controlled** study to assess putative differences in the effect of interleaving stimulation and empirical stimulation with regards to post-operation dyskinesia control.

2. Study design

2.1 Purpose

The primary objective is to assess putative differences in the effect of interleaving stimulation and empirical stimulation with regards to dyskinesia control.

2.2 Primary Outcome Measures

The changes of dyskinesia scores (UPDRS IV, item 32 + item 33) in interleaving stimulation compared to empirical programming modes. *[Time Frame: 3 months and 9*

months]

The changes of Parkinson's disease quality of life-39 (PDQ-39) scores in interleaving stimulation compared to empirical programming modes. *[Time Frame: 3 months and 9 months]*

2.3 Secondary Outcome Measures

The changes of scores of United Parkinson's Disease Rating Scale Part III in interleaving stimulation compared to empirical programming modes. *[Time Frame: 3 months and 9 months]*

Scores of neuropsychological Battery in interleaving stimulation compared to empirical programming modes. *[Time Frame: 3 months and 9 months]*

2.4 Safety outcome Measures

Adverse events *[Time Frame: up to 12 months]*

Any adverse medical event from date of randomization until the date of first documented adverse event or date of death from any cause, which ever comes first, assessed up to 12 months.

Persistent dyskinesia despite optimization of parameters of stimulation is defined with severity ≥ 2 on item 32 and duration ≥ 2 (e.g., duration \geq up to 50% of the 16 hours ambulatory time) on item 33 of the unified Parkinson's disease rating scale (UPDRS) part IV.

2.5 Study population:

Indications of DBS for PD consistent with the China specific approved labeling.

Inclusion Criteria

- Patients at the age of 30–65 years old.
- Patients diagnosed as Parkinson's disease according to the UK Parkinson's Disease Society Brain Bank criteria.
- Patients at Hoehn and Yahr stage 3 or lower in the on-state and stage 2 - 4 in the off-state.
- The disease duration of 5 years or more.
- Patients with deep levodopa-responsive Parkinson's disease, and are not adequately controlled by drug therapy.

Study participants will be PD patients undergoing DBS of the subthalamic nucleus (STN). Whether or not a patient is selected for DBS surgery is determined by the patient's clinical team purely on independent clinical grounds. Only those patients who have been accepted for DBS treatment by their clinical neurologist and functional neurosurgeon will

be introduced to the project and have their details passed on to the research team for further information and formal informed consenting.

Exclusion Criteria

Exclusion criteria are: major illness or medical comorbidities, depression that is untreated but judged to be clinically significant by an investigator, cochlear implants, cardiac pacemakers, needs for diathermy, anticoagulant therapy, previous neuro-surgical procedure or ablative therapy, frank dementia according to cognitive screening, drug or alcohol abuse, being a woman of child-bearing potential, having a positive pregnancy test, or presence of a terminal illness.

Written informed consent is obtained from all patients before any study procedures were started.

3. Study Process

3.1 Randomization and masking

50 Patients will be randomly assigned to either the interleaving stimulation modes group (ISG) or the empirical stimulation modes group (ESG).

ISG: empirical stimulation for the first 3 months, followed by interleaving programming period for 6 months, and any stimulation decided by the neurologists/neurosurgeons for the final 3 months.

ESG: empirical programming for the first 9 months' period, followed by any stimulation decided by the neurologists/neurosurgeons for the final 3 months.

Patients are randomly assigned to receive either interleaving stimulation (interleaving group, 25 patients) or empirical stimulation (conventional group, 25 patients) after the enrollment, just before the implantation of the DBS device in the STN. The randomization ratio was 1:1 (Fig 1).

Randomization is done by computer-generated pairwise according to order of enrolment, so that similar numbers of patients are recruited to each study group. The chief investigator generates the randomization sequence. The randomization scheme is kept in sealed envelopes. The randomization sequence was revealed only to the unmasked clinician responsible for the stimulation programming, but not to the rater. Patients were masked to randomisation group.

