5.2 Statistical analysis

All of the statistical tests used bilateral analysis. $P \leq 0.05$ is considered to be statistically significance (excluding special conditions).

Description of quantitative indicators is used to calculate total cases, missing cases, average cases, standard deviation, minimum, maximum, median and the interquartile range.

Description of classification index is used in different groups of cases and percentage.

Full Analysis Set (FAS): this analysis includes all subjects who received any treatment and provided useful value after the baseline stage for analysis. It also includes violators of the research scheme and subjects with incomplete data who left the trial.

Per Protocol Set (PPS): this analysis includes all subjects who completed the research and complied with the scheme without any serious errors. It also includes subjects who quit the trial because of ineffective treatment.

Safety Analysis Set (SAS): this analysis set includes all subjects who enrolled in the trial, received at least one treatment and was used for safety evaluation. Safety information records from all subjects were evaluated, including adverse events and the results of lab examinations.

6. Adverse Event

6.1 definition

Adverse Event : An AE is defined as any untoward medical occurrence, regardless of its relationship to the study device (study suture) or the study procedure. An untoward medical occurrence includes any new, undesirable medical experience or worsening of a pre-existing condition, which occurs at any point from the surgery to Final Visit.

Serious Adverse Event: A Serious Adverse Event (SAE) is any AE that:

- led to a death,
- led to a serious deterioration in the health of the subject that either resulted in:
 - a congenital deformity or abnormality;
 - a life-threatening illness or injury;
 - a permanent impairment of a body structure or a body function;
 - in-patient hospitalization or prolongation of existing hospitalization;
 - medical or surgical intervention to prevent life-threatening illness or injury; or permanent impairment of a body structure or a body function.

Relationship of Adverse Events: It is the Investigator's responsibility to assess the relationship of an AE to the study procedure and study device.

The following guidelines should be used in determining the relationship of an adverse event

to the study device, study procedure, or other causality:

- NOT RELATED: The event is due to extraneous causes.

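### Allocation concealment is not assured: the chief investigator generates the sequence, no independent custodian is named, and pairing by enrolment order may make half the list deducible

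*Combined protocol and SAP*

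**What the plan says.** All the relevant text on allocation is in section 3.1, Randomization and masking.

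- Size and ratio: "50 Patients will be randomly assigned to either the interleaving stimulation modes group (ISG) or the empirical stimulation modes group (ESG"), described as "interleaving stimulation (interleaving group, 25 patients) or empirical stimulation (conventional group, 25 patients"), and "The randomization ratio was 1:1".
- Method: "Randomization is done by computer-generated pairwise according to order of enrolment", with the stated aim of similar group sizes.
- Author of the list: "The chief investigator generates the randomization sequence".
- Concealment device: "The randomization scheme is kept in sealed envelopes".
- Disclosure: "The randomization sequence was revealed only to the unmasked clinician responsible for the stimulation programming, but not to the rater". Patients are also stated to be masked.

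Randomisation takes place after enrolment, just before implantation. Under sections 3.1 and 3.2 both arms receive empirical stimulation until Month 3. Section 2.5 leaves selection for DBS to the clinical team, after which the research team takes consent. Section 4.2 has motor assessments videotaped and rated independently by two raters.

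The document does not say who holds or opens the envelopes, when the programmer sees the sequence, or whether the chief investigator also enrols, programmes or rates.

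**The concern.** A sealed envelope hides an allocation from people who have not seen the list. It hides nothing from the person who made it. If that person can also influence consent, eligibility or order of entry, knowing the next assignment can affect who joins which arm. The analysis cannot reliably undo the resulting selection bias. The opportunity exists on paper: consent follows referral to the research team, Table 1 repeats the eligibility check at V1 (the randomisation visit), and some exclusions in section 2.5 leave room for judgement, such as major illness or clinically significant depression.

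Pairing adds a second weakness. With two patients per block, knowing one arm gives the other. At entry this affects concealment. At follow-up it means that one accidental unmasking discloses two patients. The outcomes are open to expectation: PDQ-39 is completed by the patient, item 33 covers dyskinesia over the waking day and cannot be read from a clinic video, and UPDRS III and UDysRS are scored by a rater.

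**Working it through.** **Inputs (section 3.1).** N = 50; ratio 1:1; 25 per arm; allocation in pairs by enrolment order. Assumption: pairs are permuted blocks of two.

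**The plan's own figure.** 50 / 2 = 25 pairs, one patient per arm in each pair, giving 25 and 25. This matches the stated arm sizes. It is consistent with blocks of two but does not prove that reading.

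**The author of the list.** Knows 50 of 50 allocations, whatever the block size.

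**An observer who knows the pairing rule and all earlier allocations.**
- First member of each pair: right with probability 0.5, so 25 × 0.5 = 12.5 expected correct.
- Second member: determined, so 25 × 1 = 25 correct, all with certainty.
- Total: 12.5 + 25 = 37.5 of 50, or 75%.

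**An observer who knows no earlier allocation.** Each patient stays at 50:50, an expected 25 of 50.

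**Other schemes, same informed observer.** The observer guesses the arm with more places left. Values for the alternatives are from 20,000 simulated sequences; for blocks of two the simulation also returned 37.5.

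| Scheme | Certain | Guessed correctly |
|---|---|---|
| Blocks of 2 | 25 | 37.5 (75%) |
| Blocks of 4 | about 16 | 35.1 (70%) |
| Blocks of 6 | about 12 | 33.9 (68%) |
| Random mix of 4 and 6, observer tracks running imbalance only | not computed | 34.5 (69%) |
| One random list of 25/25 | about 2 | 28.9 (58%) |

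Moving from pairs to mixed blocks therefore gains 75% − 69% = 6 percentage points against this observer, and nothing against the author of the list.

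**When treatment could reveal an arm.** Randomisation is just before implantation, switch-on is 28 ± 5 days after it, and the arms first differ three months after switch-on. Treatment cues are therefore absent for about four months after randomisation. They could inform enrolment only if the partner entered later than that. They could inform rating after Month 3, including at the Month 9 assessment.

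**Author against disclosure statement.** The statement that the chief investigator generates the sequence and the statement that only the programmer is told it are compatible if the two are the same person, or if the second describes later disclosure from the envelopes. The document states neither.

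**The case against.** The strongest reply is that the plan contains real safeguards and that much of the worry argues from silence. Patients are selected for surgery before referral, and randomisation follows enrolment. The rater is expressly not told, motor assessments are rated independently by two raters from video, and patients are masked, which is the main protection for patient-reported outcomes. All of this stands as mitigation. It does not answer the concealment point, because randomising after enrolment helps only if those who enrol do not know the next assignment.

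Four stronger readings are tempting, and the document does not support them.

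- *Masked rating is broken.* Nothing makes the chief investigator or the programmer a rater. Roles may also have appeared on pages removed from the public file. What stands is that their separation is not stated.
- *Every second allocation is predictable.* That requires knowing the first arm of the pair, and only the author and the programmer are shown to have access. If two patients were enrolled first and then randomised together, the second could not be predicted at entry, although the partner link would remain at follow-up.
- *Adverse-event judgements are compromised.* Section 6.1 says "It is the Investigator's responsibility to assess the relationship of an AE to the study procedure and study device", without naming the chief investigator. Relatedness concerns a device and procedure that both arms share. This inference rests on silence.
- *Varying the blocks brings 75% down to 50%.* It does not; the table gives about 69%.

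**Conclusion.** The point holds as a gap in assured concealment; the document does not show that concealment or masking failed. The size of the first part needs no assumption about block size: the author can know all 50 allocations, and no stated rule keeps that person away from consent, eligibility or rating. The second part (25 of 50 certain, 37.5 of 50 guessed correctly) depends on two conditions: that pairs are blocks of two, and that the observer knows the first arm of each pair. The effect on rating is limited to the period after Month 3 and to a rater who has already been unmasked to one patient and knows the pairing. The change should be made, because the trial is titled double-blind, has expectation-sensitive primary outcomes, and can close the gap cheaply.

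**What to change.** In section 3.1:

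1. Have the sequence generated, and the envelopes held, by existing institutional staff who do not enrol, programme or rate. State who opens each envelope and when the programmer learns the arm. This is the main remedy.
2. Replace pairs with randomly varying permuted blocks, for example 4 and 6, with sizes not disclosed to the study team. This is secondary.
3. If enrolment has begun (the document does not say, though parts of section 3.1 are in the past tense), apply the new list to patients not yet assigned, starting after a completed pair. Document who had access to the old list, and whether they enrolled or rated.

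Cost: a revised paragraph, a new list and a new set of envelopes. Exact 25/25 is no longer guaranteed. Stopping inside a block of 6 leaves the arms at most 3 apart, or at most 2 (26 against 24) if exactly 50 are randomised, since the difference must then be even. That imbalance has a negligible effect on precision.

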3.2 Procedures

DBS devices (Medtronic, Neuromodulation, Minneapolis, USA) approved in China (Activa® RC 37086, Pocket Adapter: Model 64001 and 64002, Extension wire: 7482, DBS lead: 3387 or 3389) are implanted by use of MRI or CT fusion for targeting and microelectrode recording for target refinement, followed by intraoperative test stimulation of the DBS lead. The pulse generators were placed in a subclavicular position on the same day.

It is allowed to use existing DBS surgery equipment and is asked to physiologically refine the DBS targets based on the best medical practices. Devices implanted into patients are initially programmed (switched on) 28 ± 5 days after surgical implantation (Week 0/ Month 0).

The patients will undergo bilateral STN DBS. Management of medication is the responsibility of the investigators at each site and was not protocol driven.

[figure not shown]
Over a 3-month period, each patient's parameters of stimulation and medications for Parkinson's disease are adjusted, based on clinical need and empirical stimulation to obtain the best clinical effect, no interleaving stimulation are allowed in this period.

At Month 3, patients are settled into either condition: with the empirical stimulation parameters or with the interleaving programming.

No routine programming plan is set during month 3 to month 9, unless the patient requires adjustment of stimulation parameters due to symptoms of Parkinson's disease or adverse effects of stimulation. The stimulation mode remains unchanged during this period and records the reason and parameters of each programming.

After month 9, the programmer can adjust the stimulation mode and parameters based on clinical need. The dopaminergic therapies are maintained stable since baseline and last in the entire duration of the study.

Fig 1

3.3 Surgical procedure

All patients have stereotactic guidance for the insertion of electrodes under local anesthesia. Leksell Frame-based stereotaxy is performed in most of the patients. The image targeting and trajectory are planned based on preoperative MRI. On the day of operation, a computed tomography (CT) scan of brain with the stereotactic frame fixed to the head is performed and fused to the MRI plan in the computer planning system. Microelectrode recording (MER) is introduced to obtain neuronal discharges for neurophysiological targeting. Macrostimulation is performed in all patients for target confirmation. Deep brain stimulation electrode is implanted if satisfactory signals from MER

and response from macrostimulation are obtained. The Pulse Generator is implanted under general anesthesia after CT scan made sure the target. The DBS is usually switched on at 4 weeks(28 ± 5 days) after the operation. Movement disorder specialists take up DBS programming. In brief, Patients are settled with simple polar stimulation with combined parameters adjustment (monopolar mode, 60~90 μ s pulse width, 130~185Hz frequency and varied voltage) during the follow-up.

3.4 Programming Procedures

[figure not shown]
The settlement of stimulation parameters is best carried out by trained neurologists and depends to a large extent on personal experience. The detailed algorithms for a disease-specific programming strategy includes contact configuration adjustment and stimulation parameters selection. In general, each of the ring electrodes should be tested in a monopolar configuration with monopolar stimulation, 130 Hz frequency and 60 microseconds pulse width. Amplitude is slowly increased until satisfactory clinical benefit or manifestation of side effects. The selected contact is determined by the best clinical outcomes and largest therapeutic window. In order to achieve the best clinical effect, frequency and pulse width should be changed by motor symptoms. Stimulation frequencies of 50 Hz and 185 Hz improve all motor signs. Pulse width between 60 and 210 μ s is beneficial for improving tremor and rigidity.

All patients receive conventional programming strategies to relieve their symptoms, but some achieve suboptimal results over time. Both levodopa inducing dyskinesia and stimulation inducing dyskinesia can happen after STN DBS. A useful strategy is decreasing the stimulation or dopaminergic medication, but some patients might experience a worsening in parkinsonism as a consequence. Unsatisfactory improvement of PD symptoms and dyskinesia, including choreoathetoid and dystonic movements, can be troublesome to patients. If patients do not improve adequately or if there are intolerable adverse effects (such as dyskinesia), interleaving stimulation (ILS) is tested to improve the symptom.

ILS consists of two rapid and alternate stimulation programs with different contacts, amplitudes, and pulse width but the same frequency up to a maximum of 125Hz. Contact selection is determined by postoperative stereotactic computed tomography and clinical evaluation to achieve a balance between motor improvement and tolerable side effects. For example, ILS is successfully applied for PD motor symptoms (stimulation of subthalamic nucleus) as well as dyskinesia (additional stimulation of zona incerta).

ILS may be applied either to limit dyskinesia or else, to stimulate different brain regions with individualized settings in order to alleviate specific symptoms. In accord with previous reports, dyskinesia is improved with additional more dorsal contact in a monopolar or bipolar fashion. Stimulation adjustment with lower amplitudes in the more dorsal contact (targeting the lenticular fasciculus) and higher amplitudes in a ventral contact (targeting the STN) might be able to control dyskinesias and parkinsonism.

Based on the standard algorithms and reconstruction images, we would choose and adjust the most suitable contacts and settings for ILS for each patient to improve their PD symptoms and alleviate dyskinesia. In addition, after ILS with one contact program, which gradually increases the amplitude and pulse width as necessary, ILS with another program selecting other specific contacts and settings, according to standard algorithms, with increased amplitude and pulse width can be performed to achieve further motor benefit and avoid adverse effects.

*: reduce medications at the same time to avoid peak-dose levodopa-induced dyskinesia and/or the worsening of stimulation-induced dyskinesia; **: training the patient on to use remote control may be a valid strategy;

4. Study assessment

4.1 Efficacy assessments

The primary efficacy endpoints are the changes of dyskinesia scores and the changes of PDQ-39 scores in interleaving stimulation compared to empirical programming modes. *[Time Frame: 3 months and 9 months]*

The secondary endpoints include the changes of UPDRS III scores and the changes of neuropsychological Battery scores in interleaving stimulation compared to empirical programming modes. *[Time Frame: 3 months and 9 months]*

The parameters in primary and secondary endpoints are also tested at baseline (Enrollment). After DBS activation (Month 0), patients are again assessed at Month 3, Month 9 and Month 12 in off-medication/on-stimulation and on-medication/on-stimulation, as shown in table 1. We defined “on-medication” as roughly 60 min after a patient takes

antiparkinsonian medication when both the clinician and the patient indicate that the medication dose is effective.

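### Two primary endpoints have no decision rule, and the one stated hypothesis is called non-inferiority but requires a 0.5-point difference and is sized on another score and visit

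*Combined protocol and SAP*

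**What the plan says.** **Objective (Section 2.1).** "The primary objective is to assess putative differences in the effect of interleaving stimulation and empirical stimulation with regards to dyskinesia control". Quality of life is not mentioned.

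**Endpoints (Sections 2.2 and 4.1).** The first primary outcome is "The changes of dyskinesia scores (UPDRS IV, item 32 + item 33) in interleaving stimulation compared to empirical programming modes". The second is the change in PDQ-39. Section 4.1 joins them with a bare conjunction: "The primary efficacy endpoints are the changes of dyskinesia scores and the changes of PDQ-39 scores in interleaving stimulation compared to empirical programming modes". Each is listed for Months 3 and 9. Section 4.1 labels the Enrollment assessment as baseline but does not say that change in these two endpoints is measured from it.

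**Treatment by period (Sections 3.1 and 3.2).** The interleaving arm receives "empirical stimulation for the first 3 months, followed by interleaving programming period for 6 months", and of the first three months Section 3.2 says "no interleaving stimulation are allowed in this period". The empirical arm stays on empirical programming to Month 9. Both arms then have "any stimulation decided by the neurologists/neurosurgeons for the final 3 months".

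**Hypothesis and sizing (Section 5.1).** The sample size uses the change from baseline in total UPDRS IV at Month 12. Under a non-inferiority heading, the hypothesis is then written for items 32+33 with no visit named. H0 puts the difference (interleaving minus empirical) below 0.5, and H1 puts it at 0.5 or more. Alpha is one-sided 0.025, power 80% and SD 1.1. Rejecting H0 is said to establish non-inferiority.

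**Analysis (Section 5.2).** All tests are two-sided at P ≤ 0.05, with an exception clause that is not defined. No test or model is named for either primary endpoint, and there is no multiplicity rule.

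**The concern.** Two primary endpoints at two visits need a rule that says which result decides the trial. The endpoint sections give none. Section 5.1 gives a hypothesis for one endpoint only, and that hypothesis contradicts its own label and is sized on a different score and visit. What counts as success could therefore be settled after the data are seen, and the candidate readings give opposite verdicts on the same data.

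The sign is also open. Section 2.4 defines persistent dyskinesia by high values on items 32 and 33, so higher is worse. If change means follow-up minus baseline, H1 as printed says that interleaving is worse by at least 0.5 points.

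**Working it through.** **Inputs.** Section 5.1 gives SD 1.1, limit 0.5, one-sided alpha 0.025, power 0.80 and 42 evaluable patients. That is 21 per arm at the 1:1 ratio of Section 3.1. Section 5.2 gives two-sided 0.05. Assumptions: SD 1.1 applies to items 32+33 at the deciding visit, the arms are independent, and positive favours interleaving. The documents give no correlation between the endpoints, so I use 0 to 0.7.

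**1. The plan's own figure.** The printed formula gives (1.960 + 0.842)² × 1.1² / (2 × 0.5²) = 7.849 × 1.21 / 0.5 = 18.99, so 19 per group and 38 in total. With the noncentral t distribution (N − 2 df) in place of the normal, the total is 41, so 21 per arm and 42. The stated 42 is reproduced. The independent-samples method that the text names gives 2 × 7.849 × 1.21 / 0.25 = 75.98, so 76 per arm. That is a separate issue; only the planned 21 per arm is used below.

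**2. Observed difference needed for success.** SE = 1.1 × √(2/21) = 0.3395; t(0.975, 40 df) = 2.021; 2.021 × 0.3395 = 0.686.

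| Reading | Calculation | Needed |
|---|---|---|
| Usual non-inferiority, margin 0.5 | −0.5 + 0.686 | 0.19 |
| No difference, two-sided 0.05 | 0 + 0.686 | 0.69 |
| Section 5.1's H0, one-sided 0.025 | 0.5 + 0.686 | 1.19 |

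An observed 0.6 passes the first and fails the other two.

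**3. One further reading.** Section 5.1 also says in words that H0 is rejected when the mean change in one arm exceeds the other's by 0.5 or more. If that is a rule on the observed means, the threshold is 0.50. It is met with probability 1 − Φ(0.5/0.3395) = 1 − Φ(1.473) = 7.0% when there is no true difference, and 50% when the true difference is 0.5. Neither is 2.5%.

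**4. Power.** For a two-sided 0.05 test with a true difference of 0.5, the noncentrality is 0.5/0.3395 = 1.473. With 40 df the power is 30%.

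**5. False claims if either endpoint at Month 9 suffices**, neither being truly affected (bivariate normal):

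| Correlation | Either direction | Benefit only |
|---|---|---|
| 0 | 1 − 0.95² = 9.75% | 1 − 0.975² = 4.9% |
| 0.7 | 8.3% | 4.2% |
| One test, for reference | 5% | 2.5% |

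If both are required, the either-direction rate is 0.25% to 1.7%. If dyskinesia alone decides, it is 5%.

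**6. What each visit can show.**

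| Visit | Interleaving arm | Empirical arm |
|---|---|---|
| Month 3 | empirical only so far | empirical only so far |
| Month 9 | six months of interleaving | empirical |
| Month 12 | any mode since Month 9 | any mode since Month 9 |

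Only Month 9 ends the randomized contrast.

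**The case against.** Several stronger readings are tempting, and the documents do not support them.

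- **The error rate is nearly doubled.** No section says that either endpoint suffices. The text leans towards dyskinesia, which is the only outcome in the objective and the only one with a hypothesis. The 8.3% to 9.75% also counts results against interleaving. What stands is that the rule is open, not that inflation is built in.
- **Month 12 decides the trial.** Section 5.1 ties Month 12 to the sample-size calculation, and its H0 and H1 name no visit. The certain defect is a mismatch between what is sized and what is declared primary.
- **Success is declared at an observed 0.5.** That sentence may only restate H1 in words, since it follows a stated alpha and power. The 7.0% and 50% hold only on the other reading.
- **The reference for change is wholly missing.** Section 5.1 does say baseline for total UPDRS IV at Month 12, and Section 4.1 equates baseline with Enrollment. The gap concerns the declared endpoints.
- **One-sided against two-sided is a serious conflict.** One-sided 0.025 and two-sided 0.05 share a critical value in the favourable direction, and the exception clause may be meant to cover it. This is a minor inconsistency.
- **Month 3 is a futile efficacy test.** If the time frame means change from Month 3 to Month 9, there is no such test.

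It can also be said that Section 5.1 is only a sizing section. But it states when H0 is rejected and what may be concluded. If it does not govern, the plan has no decision rule at all.

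**Conclusion.** The point holds and should be fixed before analysis. The plan has no stated rule for combining its two primary endpoints, no deciding visit, and no hypothesis for PDQ-39. Its one hypothesis is incoherent: the label is non-inferiority, the alternative is superiority by a margin, the sign is undefined, and the sizing uses another score at a visit outside the controlled comparison.

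The size of the problem is the sixfold spread in the success threshold, 0.19 to 1.19 points (1.186/0.186 = 6.4), given SD 1.1, 21 per arm and a sign favouring interleaving. Error inflation is conditional on an either-endpoint rule that the plan neither states nor excludes.

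**What to change.** Reconcile Sections 2.2, 4.1, 5.1 and 5.2 on one primary test:

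- **Test.** Between-arm difference in items 32+33 at Month 9, superiority, two-sided 0.05. This matches the Section 2.1 objective of assessing differences in dyskinesia control.
- **Model.** ANCOVA on one pre-named score, either Enrollment or Month 3, with the other as a sensitivity analysis. Month 3 is likely more precise but must be stated to be rated before any mode switch; Table 1 lists rating and programming at that visit without an order. It also follows three months of programming by a clinician who may know the allocation: "The randomization sequence was revealed only to the unmasked clinician responsible for the stimulation programming, but not to the rater", with no time of disclosure given. Enrollment precedes all programming.
- **PDQ-39.** Test at Month 9 only if dyskinesia is significant, or use Holm if the two are meant to carry equal weight.
- **Other visits.** Report Month 3 as a pre-switch baseline and Month 12 as descriptive.
- **Section 5.1.** Replace the non-inferiority label and H0/H1 with this hypothesis, define the sign of the difference, and restate the power for this endpoint and visit in place of 80%.
- **Section 5.2.** Define or delete the exception clause, and name the primary analysis set.

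**Cost.** This is wording plus a stated rating order at Month 3. Table 1 already schedules UPDRS IV and PDQ-39 at Enrollment, Month 3 and Month 9. Section 4.2 names MDS-UPDRS, so confirm that items 32 and 33 of the UPDRS are what is scored.

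The stated power becomes less favourable: about 30% unadjusted for a true 0.5-point difference. Adjusted for Month 3 it is 34% to 72%, and for Enrollment 21% to 46%. These ranges depend on what SD 1.1 refers to and on assumed correlations with Month 9 (0.5 to 0.7 for Month 3, 0.2 to 0.4 for Enrollment). With gating, PDQ-39 goes untested whenever dyskinesia is not significant, which at 30% power is about 70% of such trials. Holm avoids that but costs some power for dyskinesia.
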